#### 9.2.7 Fibroscan®

Where available, Fibroscan® will be performed as per institution standard practice at Visits 3 and 9.

#### 9.2.8 Markers of Fibrosis

APRI score and Fib-4 score will be calculated at randomization and at end of treatment.

APRI =  $[(\text{AST in U/L}) / (\text{AST ULN in U/L})] / (\text{Platelets in } 10^9/\text{L})$

Fibrosis 4 Score =  $(\text{Age} * \text{AST in U/L}) / (\text{Platelets in } 10^9/\text{L} * \sqrt{(\text{ALT in U/L})})$ .

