### 7.1.3 Study Procedures and Assessments

#### 7.1.3.1 Screening Period (Days -56 to 0)

##### Day -56 to Day -35/Clinic Visit 1

Patients will undergo a Screening Visit up to 56 days prior to the planned first day of study treatment. Screening procedures and assessments are as follows:

- Obtain written informed consent
- Assess inclusion/exclusion criteria ([Section 7.2](#))
- Record demographics (age, full date of birth, gender, race, and ethnicity)
- Document concomitant medications
- Medical and surgical history (date of diagnosis of PFIC Types 1 or 2, prior investigational medications for PFIC, historical liver function test [LFT] values, any surgery performed, any other diagnosis, and historical liver biopsy data)
- Collect, if available, past confirmatory clinical genetic laboratory report for PFIC-1/PFIC-2 and send to central reader for review. If a historical report is equivocal, unavailable, or unobtainable, a blood sample for clinical genetic testing will be collected to determine eligibility
- Physical examination, including voluntary photography ([Section 10.2.5](#))
- Skin examination ([Section 10.2.5](#))
- Vital signs ([Section 10.2.6](#))
- eDiary training and compliance requirements; caregivers and, if applicable, patients begin daily recording of pruritus using the eDiary ([Appendix 2](#))
- Clinical chemistry ([Section 10.2.1](#))
- s-BA ([Section 9.2.1](#))
- Serum pregnancy test for girls who have reached menarche. Please see [Appendix 6](#) for contraceptive requirements
- AE monitoring

##### Day -28 to Day -7/Clinic Visit 2

A second Screening Visit will be performed. Screening procedures and assessments are as follows:

- Review concomitant medications
- Vital signs ([Section 10.2.6](#))
- Albireo PRO/ObsRO eDiary review for compliance

- Urinalysis ([Section 10.2.1](#))
- s-BA ([Section 9.2.1](#))
- International normalized ratio (INR)
- Vitamins A and E
- Urine pregnancy test for girls of who have reached menarche
- AE monitoring

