#### **Study Day 168/Clinic Visit 9/EOT**

The last dose of study drug is taken in the morning the day before Clinic Visit 9, and the following procedures and assessments will be performed (also performed at the time a patient prematurely withdraws):

- Review of concomitant medications
- Physical examination, including voluntary photography ([Section 10.2.5](#))
- Skin examination ([Section 10.2.5](#))
- Vital signs ([Section 10.2.6](#))
- Albireo PRO/ObsRO eDiary review for compliance
- Clinical chemistry, hematology, and urinalysis ([Section 10.2.1](#))
- s-BA ([Section 9.2.1](#))
- Autotaxin, p-C4, and A4250 PK assessment (samples will not be taken for patients  $\leq 10$  kg)
- AFP

- Vitamins A, E, and 25-hydroxy vitamin D
- Abdominal ultrasound ([Section 10.2.7](#))
- Fibroscan®, where available ([Section 9.2.7](#))
- Administer PedsQL questionnaire
- Patient/caregiver/clinician complete the PGIC and PGIS
- Urine pregnancy test for girls who have reached menarche, or serum pregnancy test for girls continuing to study A4250-008
- AE monitoring
- Evaluation of study drug compliance

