### 7.2.1 Inclusion Criteria

1. A male or female patient, with clinical diagnosis of PFIC Type 1 or 2, between the ages of  $\geq 6$  months and  $\leq 18$  years at Visit 1 with a body weight above 5 kg
2. Patient must have clinical genetic confirmation of PFIC-1 or PFIC-2 through identification of biallelic pathogenic variants in either the *ATP8B1* or *ABCB11* genes
3. Patient must have elevated s-BA concentration, specifically measured to be  $\geq 100$   $\mu\text{mol/L}$ , taken as the average of 2 samples at least 7 days apart (Visits 1 and 2) prior to randomization
4. Patient must have history of significant pruritus and a caregiver-reported observed scratching in the eDiary average of  $\geq 2$  (on 0 to 4 scale) in the 2 weeks prior to randomization
5. Patient and/or legal guardian must sign informed consent (and assent) as appropriate. Patients who turn 18 years of age (or legal age per country) during the study will be required to re-consent in order to remain in the study
6. Patients will be expected to have a consistent caregiver for the duration of the study
7. Caregivers and age-appropriate patients ( $\geq 8$  years of age) must be willing and able to use an eDiary device as required by the study

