### 9.1.3 Exploratory Efficacy Endpoints

Exploratory efficacy endpoints are compared to placebo and include the following:

- Assessment of Global Symptom Relief at Weeks 4, 12, and 24 as measured by patient, caregiver, and clinician via the PGIC items ([Appendix 3](#))
- Change from baseline in fasting s-BA at Week 4

- Change in pruritus, as indexed by caregiver-reported observed scratching, from baseline by each 4 week-interval of the Treatment Period as measured by the Albireo ObsRO instrument
- Change from baseline by each 4-week interval of the Treatment Period in patient-reported and observer-reported night time itching and scratching severity scores, respectively
- Change from baseline by each 4-week interval of the Treatment Period in patient-reported and observer-reported morning time itching and scratching severity scores, respectively
- Change from baseline by each 4-week interval of the Treatment Period in pooled pruritus score including observer-reported scratching for patients <8 years of age and patient-reported itch severity for patients  $\geq 8$  years of age
- Change from baseline by each 4-week interval of the Treatment Period in additional patient-reported and observer-reported sleep parameters (e.g., tiredness and number of awakenings)
- Change from baseline to Week 24 in PedsQL ([Appendix 4](#))
- Change from baseline in serum ALT concentration at Week 4
- Change from baseline in total bilirubin at Weeks 4, 12, and 24
- Change from baseline in AST and GGT at Weeks 4, 12, and 24
- Change from baseline for other biochemical markers and measures of bile acid synthesis (autotaxin, p-C4) at Week 24
- Change in pediatric end-stage liver disease/model for end-stage liver disease (PELD/MELD) score, AST to platelet ratio index (APRI) score, and Fib-4 score from baseline to Week 24
- Change from baseline to Week 24 in stage of liver fibrosis as assessed by Fibroscan® (where available)
- Liver-related mortality and liver decompensation events
- All-cause mortality

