#### 9.2.6 PELD/MELD Score

At randomization and end of treatment, PELD score will be calculated for children up to 12 years of age. For children 13 years or older, the MELD score will be calculated.

PELD Score =  $4.80 * \ln(\text{total bilirubin}) + 18.57 * \ln(\text{INR}) - 6.87 * \ln(\text{albumin}) + 4.36$  (if patient <1 year: scores for patients listed for liver transplantation before the patient's first birthday continue to include the value assigned for age (<1 year) until the patient reaches the age of 24 months) + 6.67 (if the patient has growth failure [ $\leq 2$  SD])

Laboratory values less than 1.0 will be set to 1.0 for the calculation of the PELD score.

MELD Score =  $9.57 * \ln(\text{creatinine}) + 3.78 * \ln(\text{total bilirubin}) + 11.2 * \ln(\text{INR}) + 6.43$

Laboratory values less than 1.0 will be set to 1.0 and serum creatinine values greater than 4.0 mg/dL (equivalent to 353.6  $\mu\text{mol/L}$ ) will be set to 4.0 for calculation of the MELD score.

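### The Week 24 change in PELD/MELD, and in Fib-4 on its natural reading, mixes growing older and switching formula with liver status

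*Protocol*

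**What the plan says.** Section 9.2.8 defines Fib-4 with age as a direct multiplier: age times AST, divided by platelets times the square root of ALT. It sets two time points: "APRI score and Fib-4 score will be calculated at randomization and at end of treatment". APRI, in the same section, contains no age.

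Section 9.2.6 sets the same two time points for PELD/MELD. PELD applies up to 12 years, and "For children 13 years or older, the MELD score will be calculated". PELD adds 4.36 points below 1 year of age. Only patients listed for transplant before their first birthday "continue to include the value assigned for age (<1 year) until the patient reaches the age of 24 months". PELD also adds 6.67 points for growth failure. MELD has neither term.

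Section 9.1.3 takes as exploratory endpoints, compared with placebo, the change in PELD/MELD, "AST to platelet ratio index (APRI) score, and Fib-4 score from baseline to Week 24". Section 11.2.2.6 says these are analyzed descriptively, with the change from baseline shown in addition to the visit values.

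No section says that the formula, the infant term or the age in Fib-4 is held at its baseline state when the change is formed.

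**The concern.** A change from baseline in a liver score should move only when the liver measurements move. Applied literally, these rules make it move with the calendar, and in different directions at different ages. Fib-4 drifts upward (apparent worsening) in every child. PELD drops (apparent improvement) at the first birthday. The move from PELD to MELD at 13 produces a large rise, because values of two different formulas are subtracted.

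The trial enrols from 6 months of age, where the ageing term in Fib-4 is largest. With about 20 patients per arm, a single child crossing 13 visibly shifts an arm mean. Chance age differences between arms, including differences within an age class, then feed into the comparison with placebo.

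**Working it through.** The protocol gives no figure for the effect of age, so there is nothing to reproduce. The check holds laboratory values fixed and applies the formulas of 9.2.6 and 9.2.8.

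**Inputs**
- Lowest age: 6 months (182.6 days), tested in 7.2.1 in "years at Visit 1 with a body weight above 5 kg", so at Visit 1 and not at randomization.
- Visit 1 precedes randomization by 35 to 56 days (7.1.3.1, "Day -56 to Day -35/Clinic Visit 1"). The ±2-day window in Table 1 makes this at least 33 days.
- Follow-up is 168 days, ±3 (7.1.3.2, "Study Day 168/Clinic Visit 9/EOT").
- Laboratory values below 1.0 are set to 1.0 (9.2.6).
- Assumed, because the documents give no patient values: bilirubin 1 to 5 mg/dL, INR 1.0 to 1.2, albumin 3.5 to 4.2 g/dL, creatinine below 1 mg/dL. The current 9.2.6 gives no units for bilirubin or albumin. The version dated 15 March 2018 gives mg/dL and g/dL.

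**Switch at 13.** With creatinine set to 1,

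MELD − PELD = 6.43 + 6.87·ln(albumin) − 1.02·ln(bilirubin) − 7.37·ln(INR) − 6.67 (if growth failure).

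- Bilirubin 3, INR 1.1, albumin 4.0: PELD = 4.80·ln 3 + 18.57·ln 1.1 − 6.87·ln 4 = −2.48. MELD = 3.78·ln 3 + 11.2·ln 1.1 + 6.43 = 11.65. Difference +14.13.
- Bilirubin 5, INR 1.2, albumin 3.5: +12.05.
- Bilirubin 1, INR 1.0, albumin 4.0: +15.95 (with albumin 4.2, +16.3).
- With growth failure each value is 6.67 lower: +7.46, +5.38 and +9.28 (with albumin 4.2, +9.6).
- Over a wider assumed range (bilirubin 0.5 to 6, INR 1.0 to 1.4, albumin 3 to 5): +9.7 to +17.5 without growth failure, +3.0 to +10.8 with it.

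One such child in an arm of 20 moves the mean by 14.1/20 = 0.7 points, or 7.46/20 = 0.4 with growth failure. If birthdays are uniform, 168/365.25 = 46% of 12-year-olds turn 13 on study. If 20 children fall in the 6-to-12 class with ages spread evenly, about 20/7 = 2.9 are aged 12 and about 1.3 cross in the whole trial, fewer than 0.5 per arm.

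**Infant term.** The youngest possible child at the earliest Week 24 visit is 182.6 + 33 + 165 = 380.6 days old, past the first birthday. So every child under 1 year at randomization who reaches Week 24, and was not listed for transplant before the first birthday, loses 4.36 points. On the PELD scale this equals a fall in bilirubin by a factor of exp(4.36/4.80) = 2.5.

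**Fib-4 with age at each visit.** Relative change = days of follow-up / age in days at randomization.

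| Age at randomization | Rise from ageing alone |
|---|---|
| Youngest possible, 182.6 + 35 = 217.6 days | 168/217.6 = 77% |
| Same, all windows at their extreme | 171/215.6 = 79% |
| 1 year | 46% |
| 2 years | 23% |
| 5 years | 9% |
| 10 years | 5% |

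If age and formula are held at randomization, all three artefacts are exactly 0.

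**The case against.** The strongest reply concerns Fib-4. Section 9.2.8 says only age, without saying at which date or whether in decimal or completed years, and 11.2.2.6 leaves further detail on exploratory variables to the SAP. That stands in part: attained age is the natural reading of a score calculated at each visit, but it is an inference. The reply does not reach PELD/MELD, where 9.2.6 itself fixes the cut-off at 13, the infant term and both time points.

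The second reply is limited impact, and much of it stands. The scores are exploratory, summarized descriptively and carry no alpha. Ageing acts in every arm, randomization is stratified by age class (8.3.3), and few children would cross 13. Stratification is only partial protection. The youngest class runs from an ageing effect of about 77% down to 9% at age 5, the patients from Study A4250-003 are randomized on a separate list regardless of strata, and balance between arms does not repair a within-arm change.

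Several stronger readings are tempting and not supported:
- A reader might put the Fib-4 maximum at 168/182.6 = 92%. That needs a child aged exactly 6 months at randomization, and the age limit applies at least 33 days earlier.
- A reader might think only infants beyond some age at randomization lose the 4.36 points. All who reach Week 24 pass the birthday.
- A reader might take +12 to +16 as general. It holds only without growth failure and on assumed laboratory values and units.
- A reader might conclude that ageing outweighs any drug effect or biases the comparison with placebo. The documents give no expected effect or SD for these scores.
- A reader might note that in completed years Fib-4 is 0 in infants and doubles from age 1 to 2. That is true of that convention, but nothing in the text selects it.

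**Conclusion.** The point holds for PELD/MELD as written, and for Fib-4 on its natural reading. The stated rules give a change score that moves with no change in laboratory values: 4.36 points down in every unlisted infant followed to Week 24; about 12 to 16 points up in a child turning 13 without growth failure, or about 5 to 10 with it; and a Fib-4 rise of at most about 77% (79% at extreme windows), falling to about 5% by age 10. The infant figure follows from the text alone. The figures for the switch at 13 rest on the assumed laboratory values and units, and the Fib-4 figures on attained decimal age. The consequence is minor: distorted within-arm changes and added noise in exploratory, descriptive summaries. It does not touch the primary endpoints.

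**What to change.** In 9.2.6, add that for the change from baseline the choice of PELD or MELD and the under-1-year term are set by age at randomization and applied at both visits. In 9.2.8, add that for the change from baseline Fib-4 uses exact decimal age at randomization at both visits.

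The cost is one sentence in each section and no new data. Albumin, bilirubin and creatinine are all in the clinical chemistry panel at both visits, so holding a child on the baseline formula asks for no added chemistry. The downside is that Week 24 absolute values computed this way are not the score for the child's current age, so tables must label them as using baseline age.

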#### 9.2.9 Global Impression of Change and Global Impression of Symptom Measures

Patients ( $\geq 8$  years of age), caregivers, and clinicians will complete the PGIC and the PGIS measures ([Appendix 3](#)) at randomization (Visit 3; PGIS only), Visits 4 and 6, and at EOT (Visit 9).

The PGIC items assess change in itch (patient version), scratching (caregiver and clinician versions), and sleep (all versions) since starting the study drug. The PGIS items assess itch

(patient version), scratching (caregiver and clinician versions), and sleep (all versions) in the past week. Caregivers and clinicians will complete the PGIC and PGIS for all patients; those patients  $\geq 8$  years of age will complete the patient version.

## 10 ASSESSMENT OF SAFETY

The timing and frequency of safety assessments are described in [Section 7.1.3](#) and in [Table 1](#) above.

The primary safety analysis for this study will include the incidence of total treatment-emergent adverse events (TEAE) and TEAEs categorized by causality, severity, and seriousness assessments made by the investigator by comparing study drug exposure to placebo.

Trends in safety will also be evaluated for the following assessments:

- Physical examinations
- Concomitant medications
- Vital signs
- Laboratory test results (including clinical chemistry, hematology, urinalysis, AFP, and vitamins A and E, 25-hydroxy vitamin D, and INR)
- Abdominal ultrasound
- Discontinuations due to AEs

### 10.1 Adverse Events

#### 10.1.1 Definitions and Investigator Assessments

An AE is defined as any untoward medical occurrence in an enrolled patient regardless of causal relationship with study drug. An AE can therefore be any clinically significant unfavorable and unintended sign, symptom, or disease that occurs once a patient is enrolled (ICF is signed) in the study until the patient is discharged from the study, whether or not related to the study drug.

##### 10.1.1.1 Clinical Significance

Clinical significance is defined as any abnormal finding that results in further clinical investigation(s), treatment(s), or the diagnosis of new condition. Patient-reported events and protocol-mandated laboratory values, vital signs, and physical examination findings can be considered clinically significant (i.e., an AE) if there is a deterioration as compared to baseline. Examples of clinically significant worsening from baseline could include, but is not limited to, events causing withdrawal from the study and events requiring medical intervention outside of the study causing apparent clinical manifestations, or judged relevant by the investigator.

##### 10.1.1.2 Serious Adverse Events

Serious criteria are applied by the investigator to each AE as specifically defined below. These criteria are used to determine whether an AE is serious or non-serious. The assessment

is made independently of severity assessment (Section 10.1.1.3). For example, the development of a severe rash that occurs after signing of informed consent may not meet serious criteria as defined below and therefore would be considered a severe, non-serious AE.

Any AE that meets any 1 of the following 6 criteria is considered an SAE:

- The outcome of the AE is **death**
- The AE is immediately **life-threatening**. Life-threatening means that the patient is, in the opinion of the investigator, at immediate risk of death from the reaction as it occurred. This does not include an AE that, if more severe, might have caused death
- The AE results in persistent or significant **disability/incapacity**. Disability means a substantial disruption of a person's ability to conduct normal life functions
- The AE requires or prolongs **hospitalization**
- The AE results in a **congenital anomaly/birth defect**
- **The AE is an important medical event**. Important medical events may meet serious criteria should the investigator assess that they may significantly jeopardize the patient, represent a significant hazard, or requires medical/surgical intervention to prevent one of the outcomes listed above. Examples of potential SAEs based on this criteria include, but are not limited to, allergic bronchospasm requiring intensive treatment in an emergency room or at home, blood dyscrasias or convulsions even if they do not result in inpatient hospitalization, or the development of drug dependency and drug abuse.

#### 10.1.1.3 Severity Assessment

Severity assessments are based on the intensity of the event in relation to expectation. The investigator will assess the intensity of AEs based on the following definitions:

- Mild (awareness of sign or symptom, but easily tolerated)
- Moderate (discomfort sufficient to cause interference with normal activities)
- Severe (incapacitating, with inability to perform normal activities)

Severity is a measure of intensity where seriousness is defined by the criteria outlined in [Section 10.1.1.2](#). An AE of severe intensity need not necessarily be considered serious. For example, nausea that persists for several hours may be considered severe nausea, but not meet serious criteria, and therefore would be assessed as a severe AE but not an SAE.

#### 10.1.1.4 Causality Assessment

The investigator determines the causality of all AEs to the study drug using medical judgment and considering all relevant factors such as (but not limited to) the underlying study indication, coexisting disease, concomitant medication, relevant history, pattern of the AE, temporal relationship to the study drug, and de-challenge or re-challenge. The causality assessment of the AE/SAE is to be made as follows.

### **Related to study drug (possibly, probably, or definitely related)**

Based on medical judgment, there is at least a reasonable possibility that the study drug caused the event; one or more of the following criteria apply:

- The event follows a reasonable temporal sequence from administration of study drug
- The event could not be reasonably attributed to the known characteristics of the patient's clinical state, environmental or toxic factors, or other modes of therapy administered to the patient
- The event follows a known pattern of response to study drug
- The event disappears or decreases on cessation or reduction in dose of the study drug. (It should be noted that in some situations an AE will not disappear or decrease in intensity upon discontinuation of study drug despite other clear indications of relatedness)
- The event reappears or worsens when the study drug is re-administered

### **Unrelated to study drug (unlikely or unrelated)**

Based on medical judgment there is no reasonable possibility that the study drug caused the event; one or more of the following criteria apply:

- The event does not follow a reasonable temporal sequence from administration of study drug
- The event could be reasonably attributed to the known characteristics of the patient's clinical state, concurrent illness, environment or toxic factors, or other modes of therapy administered to the patient
- The event does not follow a known pattern of response to study drug
- The event does not disappear or decrease on cessation or reduction in dose of the study drug, and it does not reappear or worsen when the study drug is re-administered

#### **10.1.2 Recording of Adverse Events**

It is the investigator's responsibility to assess whether each untoward event is a clinically significant worsening from baseline, thereby considered an AE. For all AEs, the severity, seriousness, and causality to study drug for each AE as outlined in [Section 10.1.1](#) will be assessed and recorded in the eCRF.

All serious and non-serious AEs are collected once the caregiver/patient has signed the ICF and until the post-treatment follow-up (Visit 10) or 28 days after the last dose of study drug.

Any AEs or SAEs that are unresolved at the patient's last AE assessment in the study are followed up by the investigator until resolution or stabilization up to the database lock and recorded in the eCRF. Albireo retains the right to request additional information for any patient with ongoing AE(s) or SAE(s) at the end of the study.

TEAEs are defined as any AE that occurs after randomization (Day 0). All AEs that occur in the Screening Period, i.e., after enrollment and prior to randomization, will be collected on the eCRF as non-treatment-emergent AEs.

If there is a clinically significant deterioration of a laboratory value/vital sign or other routine study assessment that is associated with a diagnosis, the clinical diagnosis will be reported as an AE and the associated signs and symptoms will be considered additional information unless the sign or symptom is more severe than expected given the diagnosis. For example, if an investigator diagnoses a study patient with hepatitis during the study period, hepatitis would be considered the AE and the concomitant signs and symptoms of abdominal pain, vomiting, and elevated ALT and AST would not be reported separately unless, in the opinion of the investigator, one of these signs or symptoms is more severe than expected and therefore a separate AE assessment is indicated.

